
### **Control Group**

The control group will not receive a prescribed physical therapy intervention and will be instructed to go about their daily lives as usual. They will be asked to avoid making changes to their daily routine or usual exercise program. Participants will be allowed to adjust anti-PD

## Physical Therapy and Deep Brain Stimulation in Parkinson Disease (PTDBS)

medication and STN-DBS settings as determined by their neurologist. To measure safety, those assigned the control group will be called weekly and will complete the Adverse Events tracking form over the phone with a member of the study team.

### **Follow-Up Testing**

The 8-week and 12-week follow up visits will occur as soon as possible after the intervention is completed. The same protocol completed at baseline will be followed for this assessment. Again participants will be tested in the OFF stimulation / OFF medication and ON stimulation / ON medication conditions on two separate days. The OFF stimulation / OFF medication visit will last approximately 3 hours and the ON stimulation / ON medication visit will last approximately 2 hours.

### **Randomization Method**

Participants will be randomly assigned (1:1 ratio) to either the PT intervention group or the control group in a consecutive fashion using an internet randomization scheme generator. A study team member will write the group assignment number on a piece of paper wrapped in tin foil. This will be placed in an opaque envelope and sealed. After participants complete both baseline assessment they will be allowed to open the envelope to determine their group assignment.

### **Safety and Adverse Events**

The research team will do everything possible to ensure safety of all participants over the course of this study. Potential adverse events related to this study may include falls with serious injury, major cardiovascular incidents, or serious injuries associated with physical activity. The Adverse Event tracking form will be completed weekly with every participant. The adverse event most likely to occur in this study is a participant fall due to walking. Members of the research team will all be trained in fall prevention and will closely monitor all participants throughout all aspects of the study in case of a need to assist with balance to prevent a fall. In the case of a serious adverse event, emergency medical care will be sought immediately if needed. Any serious adverse events will be reported to the local IRB in accordance with their policies and procedures.

These risks will be addressed in the following ways:

- a) Effects of withholding overnight and morning anti-PD medications: Participants may experience a temporary worsening of your Parkinson's disease symptoms as a result of not taking their anti-Parkinson's medication for study evaluations. Once taking the medication, the symptoms should return to their typical levels. Effects of medication withdrawal will be monitored and if the effects are too severe, participants will immediately take their medication. At that point, the study will be discontinued.
- b) Effects of turning off deep brain stimulators: Participants may experience a temporary worsening of your Parkinson's disease symptoms as a result of turning off the deep brain stimulators for study evaluations. Once we turn the stimulators on, the symptoms should return to their typical levels. Effects of stimulation withdrawal will be monitored and if the effects are too severe, participants will immediately have their stimulators turned on. At that point, the study will be discontinued.

## Physical Therapy and Deep Brain Stimulation in Parkinson Disease (PTDBS)

- c) Loss of confidentiality: Loss of confidentiality is highly unlikely. To safeguard against this, we will comply with all HIPAA regulations. Data will not be identified by subject name. All data will be coded, and code sheets will be stored in locked files.
- d) Stumbling during locomotion: Participants will be closely attended by a physical therapist during the assessment and physical therapy intervention. Walking, during the assessments, will be performed in a large, open space and the therapist will be prepared to assist participants who may stumble. Walking during the intervention will be performed on a treadmill and participants will be instructed to hold onto the railing for stability and will be guarded by a physical therapist to reduce fall risk. The treadmill is equipped with several safety features that allow the participant or physical therapist to stop the treadmill immediately. Each participant will be oriented to the safety features prior to commencing treadmill walking and these will be reviewed at each intervention session. It is therefore unlikely that participants will experience falls during testing or will be injured as the result of a fall. If a fall were to occur, the physical therapist will provide immediate first aid as needed using a first aid kit within the Movement Science Research Center. The physical therapist will also assess for the need for emergency medical care and will call [contact] (Washington University Security Services) to arrange for emergency transportation to the Barnes Jewish Hospital Emergency Department as needed.
- e) Falling during locomotion: Participants will be closely attended by a physical therapist and/or trained assistant who will ensure the safest of conditions. It is unlikely that participants will experience falls during assessment or exercise or will be injured as the result of a fall. If a participant appears unsteady, breaks will be encouraged or testing will be terminated. If a fall were to occur, the physical therapist will provide immediate first aid as needed using a first aid kit within the Movement Science Research Center. The physical therapist will also assess for the need for emergency medical care and will call [contact] (Washington University Security Services) to arrange for emergency transportation to the Barnes Jewish Hospital Emergency Department as needed.
- f) Fatigue: Rest breaks will be provided as frequently as possible.
- g) Muscle soreness: Rest breaks will be provided as frequently as possible.
- h) Skin irritation from activity monitor: Participants will be instructed in how to correctly don and doff the monitors. The participants will also be instructed in how to monitor for any skin irritation that might be associated with wearing the monitors. Participants will be instructed that if they have noticeable skin irritation (i.e. redness, discomfort) they should doff the monitors.
- i) Fatigue and/or loss of balance during home exercise program: The home exercise program will include only 3 exercises: sit-to-stand, standing heel raises, and standing partial squats. Regarding fatigue, participants will be instructed to rest if they feel fatigued during the exercise program. The participants will be educated in how to perform these exercises correctly and safely. The physical therapist will require that participants demonstrate safe performance of the exercise before clearing them to do the home exercise program. For sit-to-stand, participants will be instructed to place a chair against a wall so that the chair doesn't have room to move backward thus avoiding a potential fall. For both the heel raises and squats, participants will be instructed to only do these exercises when holding on to a counter or sink at home that is fixed to the wall. This will provide stable upper extremity support minimizing the risk for any loss of balance.
- j) Major cardiac event during physical activity: The cardiac risks in this study are minimal because the exercise intervention will not be of high intensity. To ensure that the risk is minimal, we will obtain a physician's note prior to the start of intervention that clears each participant for participation. Further, for those in the PT group, we will measure vital

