**Exclusion Criteria:**

- 1) Serious medical problem (aside from PD)
- 2) History or evidence of other neurological deficits, such as previous stroke or muscle disease
- 3) History or evidence of orthopedic, muscular, or psychological problem that prevents participation in either intervention
- 4) Inability to walk 10 meters with or without assistive device

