#### Protocol

A phone screen will be used to screen study candidates for eligibility. All eligible participants will be scheduled to start the study as soon as they are able at a time that is convenient to both the participant and the research team.

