## Physical Therapy and Deep Brain Stimulation in Parkinson Disease (PTDBS)

### **Baseline Testing**

Baseline testing will be conducted with participants in two conditions: 1) OFF stimulation / OFF medication, 2) ON stimulation / ON medication. These conditions will be tested on two separate days within one week of each other and the order of conditions will be randomized. The OFF stimulation / OFF medication and ON stimulation / ON medication testing sessions will occur on two separate days to avoid fatigue. Regardless of testing condition, upon arriving for the first laboratory visit, informed consent will be obtained from each participant.

**Informed Consent and MMSE:** Participants will be consented in a private room with only the participant and study team members present. Participants will first receive a verbal explanation of the study and then be given as much time as they wish to read the consent form and ask any questions they may have. Participants will provide written informed consent prior to commencing study participation.

The Mini-Mental Status Examination (MMSE) will be conducted first only in the ON stimulation / ON medication condition. If the participant scores less than 24/30, the participant will be excluded from further participation at this time. If the score is 24 or above, the baseline assessment will proceed. After completing the MMSE in the ON stimulation / ON medication condition, each participant will complete the battery of balance, walking, and motor function tests.

For the OFF stimulation / OFF medication condition, participants will arrive to the laboratory in the practically defined off-state of their medication cycle (i.e.  $\geq 12$  hours since last dose). The deep brain stimulators will be turned off and the participant will then wait 45 minutes until the physical assessment begins. After 45 minutes, each participant will complete a battery of balance, walking, and motor function tests.

Upon completion of the baseline visits, the participant will be randomized to either the intervention or control group.

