### **Intervention**

Within one week of the initial visit, for the participants assigned to the PT group, the PT intervention will begin. Participants in the PT group will receive 8 weeks of the intervention, meeting 2 times per week for one hour each session.

**Physical Therapy:** This intervention will mirror traditional physical therapy for individuals with PD and will include exercises designed to improve balance, gait, and lower extremity strength. Balance exercises will follow a framework outlined by Schoneburg and colleagues targeting quiet stance, anticipatory and reactive postural adjustments, and dynamic postural control. Quiet stance exercises might include, but are not limited to, standing on a firm surface with eyes closed, standing on a foam surface with eyes closed, and standing in tandem (one foot in front of the other). Anticipatory postural adjustment exercises might include, but are not limited to, standing on one leg, sit-to-stand, and trunk rotation in standing with feet planted. Reactive postural adjustment exercises might include, but are not limited to, standing with perturbations from the physical therapist while on firm and foam surfaces and leaning forward, backward, or laterally and taking a step to regain balance when needed. Dynamic postural control exercises might include, but are not limited to, walking with head turns side-to-side, walking while bouncing a ball, and walking around

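### The physician's note is due only before the intervention starts, so the plan allows a participant to be randomised to PT before clearance is known

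*Combined protocol and SAP*

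**What the plan says.** **Clearance.** Item j of the risk list under Safety and Adverse Events, on major cardiac events, says that "we will obtain a physician's note prior to the start of intervention that clears each participant for participation". The next sentence begins "Further, for those in the PT group, we will measure vital" signs, so the protocol marks that step, and not the note, as limited to the PT group.

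**Screening and eligibility.** The Protocol section says: "A phone screen will be used to screen study candidates for eligibility". The inclusion and exclusion criteria contain no physician clearance. They do exclude a serious medical problem other than PD, and orthopedic, muscular or psychological problems that prevent taking part.

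**Randomisation.** Baseline Testing says: "Upon completion of the baseline visits, the participant will be randomized to either the intervention or control group". Randomization Method adds: "After participants complete both baseline assessment they will be allowed to open the envelope to determine their group assignment".

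**Start of PT.** The Intervention section says: "Within one week of the initial visit, for the participants assigned to the PT group, the PT intervention will begin".

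**Controls.** The Control Group section says: "The control group will not receive a prescribed physical therapy intervention and will be instructed to go about their daily lives as usual". It adds a weekly adverse-event call and does not mention the note.

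**Analysis.** The Statistical Analysis Plan defines no analysis population. Nothing in the documents says what happens to a randomised participant who is not cleared.

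**The concern.** A check that can stop someone from receiving the allocated treatment belongs before allocation. If it comes later, the people it stops have already been randomised. They must then either be analysed as PT participants who had no PT or be left out, and leaving them out breaks the randomised comparison. Refusal of clearance would plausibly depend on health, so such a loss need not be random.

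The two arms are also placed differently. In the PT arm, a missing or refused note has an obvious effect: PT cannot start. In the control arm there is no intervention to start, so the plan gives neither a date by which the note is due nor a consequence if it is refused. With 17 participants per arm, one or two such cases would be visible in the adverse-event counts, the adherence percentage, and the balance and gait comparison.

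**Working it through.** The plan gives no figure on this point to reproduce. The check is first one of order, then of possible size.

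**Order of steps as written**

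1. Phone screen (Protocol). Clearance is not mentioned.
2. Consent at the first laboratory visit, then two baseline days within one week of each other (Baseline Testing). Clearance is not mentioned. The MMSE is a useful contrast: it is an inclusion criterion, it is done at baseline, and a score below 24 has a stated consequence, all before allocation.
3. Envelope opened after both baseline assessments (Randomization Method).
4. PT begins, for the PT group (Intervention).
5. Latest time for the note: before step 4 (Safety and Adverse Events, item j).

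The interval between steps 3 and 4 is therefore open. A note that arrives, or is refused, in that interval meets the protocol's wording.

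**Time available.** PT is to begin within 7 days of the initial visit. If that is the first baseline day and the second falls *d* days later (*d* from 1 to 7), the time left between allocation and the latest PT start is 7 − *d* days: 6 days at most and 0 at least. The documents do not say when the note is requested. If it is requested only after consent, it may not be in hand when the envelope is opened.

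**Possible number affected.** The inputs are 17 per group (Power) and a non-clearance rate that the documents do not give, assumed here to be 0% to 10%. The calculation takes every refusal as coming after allocation.

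| Assumed rate *p* | Expected PT participants, 17 × *p* | Chance of at least one, 1 − (1 − *p*)^17 |
|---|---|---|
| 0% | 0 | 0% |
| 5% | 0.85 | 1 − 0.95^17 = 58% |
| 10% | 1.7 | 1 − 0.90^17 = 83% |

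The Power section needs 14 per group and recruits 17, so the attrition allowance is 17 − 14 = 3. The expected numbers lie within it, but they would use part of an allowance that was set for dropout.

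**Effect on power.** This is small. Take f = 0.25, alpha 0.05, an assumed within-person correlation of 0.5 and 20% dropout in both arms. The noncentrality of the group-by-time test is f² × N × m / (1 − 0.5), where m is the number of time points and N is the effective total 4 × n1 × n2 / (n1 + n2). With no non-clearance, n1 = n2 = 17 × 0.8 = 13.6. With two PT participants lost, n1 = 15 × 0.8 = 12.0 and n2 = 13.6. Power then goes from 70.8% to 67.8% with the two time points in the Statistical Analysis Plan, or from 79.9% to 76.9% with three. Lost precision is not the main issue. Possible selective loss is, and these figures do not measure it.

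**Effect on adherence.** The Measures section defines feasibility as sessions attended out of 16, and the hypothesis is at least 80%. It does not say whether someone who never starts counts as 0 of 16. As an illustration, suppose cleared participants average 85% (assumed). Counting one non-starter as zero gives 16 × 85 / 17 = 80.0%, and counting two gives 15 × 85 / 17 = 75.0%. Leaving them out gives 85%.

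**The case against.** A reader might infer that controls have no clearance step at all. The text does not support that. The note is said to clear each participant, and only the vital-sign checks are set apart for the PT group. What is missing for controls is a due date and a consequence, not the requirement.

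A reader might also infer that notes will in fact be obtained after randomisation. That does not follow either. The deadline is a latest time, and a note collected before baseline would satisfy it. The short interval before PT makes early collection plausible. The word intervention is also used loosely: exclusion criterion 3 speaks of either intervention, and Follow-Up Testing times the visits from the end of the intervention with no separate rule for controls. So the start of intervention could be read as the start of the study period in both arms. The medical exclusions and the phone screen apply to everyone and should keep late refusals few, and item j calls the cardiac risk minimal.

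These points stand, and they limit the concern. They do not remove it. Nothing in the plan requires the note before allocation, and the Intervention section describes a start date only for the PT group.

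**Conclusion.** The point holds as a gap in procedure. The only stated deadline for clearance falls after randomisation, clearance is not an eligibility, screening or baseline step, and the plan therefore permits allocation to PT followed by failure to start for lack of a note. No due date or consequence is stated for controls.

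Its size is unknown. At an assumed 0% to 10% non-clearance, 0 to 1.7 of 17 PT participants would be affected, fewer if notes are collected early or the existing exclusions work as intended.

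It is tempting to conclude that the results would be biased in favour of PT. The documents do not support a direction for balance or gait: the test is of change over time by group, and losing frailer participants could raise or lower the mean change. Adherence is a threshold within the PT arm and not a comparison between arms. Adverse events are compared only qualitatively. Nor do the documents say that an uncleared participant leaves follow-up or the analysis; they are silent. This is a modest improvement, worth making because it is cheap.

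**What to change.** State that the physician's note must be in hand for every participant, in both arms, before the allocation envelope is opened, and list it with the eligibility checks. The requirement and the standard for clearance stay unchanged; only the deadline moves. If the team already collects notes before baseline, this only records the practice.

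The cost is a sentence or two and possibly a few days' delay before randomisation. Because PT is to begin within one week of the initial visit and the two baseline days may themselves be up to a week apart, the sponsor must reconcile that window with the new order.

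Moving the note prevents losses after allocation for non-clearance. It does not settle how participants who do not start PT for other reasons are analysed, which is a separate gap in the Statistical Analysis Plan.

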## Physical Therapy and Deep Brain Stimulation in Parkinson Disease (PTDBS)

signs before treatment and before and after aerobic activity like treadmill walking. If a participant's vital signs are found to be outside of normal for that specific participant, aerobic exercise will not be performed and we will contact the physician to determine how to proceed. If a participant demonstrates or reports symptoms associated with a cardiac event, the intervention will stop and the physical therapist will contact emergency medical personnel.

### **Benefits**

It is unclear whether participants will benefit from participating in this study. This study will help to determine whether physical therapy might be a useful treatment option for people with PD who have DBS.

### **Interim Monitoring and Early Stopping**

Safety will be monitored throughout the study. If it is noted that the physical therapy intervention is unsafe (i.e. more than 2 falls across multiple individuals are occurring within the intervention sessions), the research team will meet to determine whether or not it is safe to continue. We will not conduct an interim data analysis to determine whether the study should continue.

### **Statistical Analysis Plan**

The total number of adverse events will be reported for each group allowing for qualitative comparisons.

Adherence will be reported for both attendance of PT and control sessions and will be expressed as percent of sessions completed.

Balance and gait data will be analyzed using mixed models with repeated measures or appropriate non-parametric test as appropriate to test for main effects of group (PT, control) and time (baseline, 8-weeks) and group\*time interactions ( $\alpha \leq 0.05$ ).

If there are baseline differences in demographic variables (e.g. age, gender, years since PD diagnosis, years since DBS), we will use these variables as covariates in the analyses.

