**Official Title: Physical Therapy and Deep Brain Stimulation in Parkinson Disease**

**NCT Number: NCT03181282**

**Document Date: May 11, 2017**

## **I. Specific Aims**

The purpose of this study is to examine the safety, feasibility, and preliminary efficacy of PT in people with PD with STN-DBS. We expect that participants with STN-DBS in the PT group will not report more adverse effects than those in the control group. Furthermore, we hypothesize that those in the PT group will complete at least 80% of prescribed PT sessions. We also expect that those in the PT group will demonstrate improvements in balance and gait while those in the control group will demonstrate no change or a decline in balance and gait.

Specific Aim 1: To determine the safety of an 8-week PT intervention in people with STN-DBS. The primary variable of interest for safety is the number of adverse events (e.g. falls, orthopedic injuries).

Hypothesis 1: We hypothesize that participants with STN-DBS plus PT will not report more adverse effects than those with STN-DBS only.

Specific Aim 2: To determine the feasibility of an 8-week PT intervention in people with STN-DBS. The primary variable of interest for feasibility is adherence to the PT intervention, measured as a percentage of PT sessions completed.

Hypothesis 2: We hypothesize that participants with STN-DBS will complete at least 80% of prescribed PT sessions.

Specific Aim 3A: To evaluate the preliminary efficacy of PT on balance in people with STN-DBS. The primary variable of interest is the Balance Evaluation Systems Test (BESTest) total score.

Hypothesis 3A: We hypothesize that participants with STN-DBS plus PT will demonstrate improvements in balance while those with STN-DBS only will demonstrate no change or a decline in balance.

Specific Aim 3B: To determine the preliminary efficacy of PT on gait in people with STN-DBS. The primary variables of interest is preferred-pace gait velocity.

Hypothesis 3B: We hypothesize that participants with STN-DBS plus PT will demonstrate improvements in preferred-pace gait velocity while those with STN-DBS only will demonstrate no change or a decline in gait.

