## Physical Therapy and Deep Brain Stimulation in Parkinson Disease (PTDBS)

an obstacle course. During every balance exercise, a physical therapist will be guarding the participant, who will be wearing a gait belt for safety. The gait belt will reduce the risk of falling by enabling the physical therapist to maintain contact with the participant at all times. Balance exercises following a similar framework improved balance and reduced falls in people with PD without STN-DBS. Balance exercises will be chosen using a decision tree to ensure exercises are sufficiently challenging to maximize the potential effect. For example, if a person is able to stand with feet together on a firm surface without significant sway on observation, the participant will then be asked to close their eyes to increase the challenge. Gait training exercises will include treadmill walking and practice with cueing strategies (e.g., auditory, visual) to improve gait and reduce freezing of gait. Treadmill walking will start at the participant's comfortable pace (measured during overground walking) and progress weekly provided the participant is able to tolerate it. Tolerance of treadmill walking will be determined by the observation of gait quality during treadmill walking and the participant's rating of perceived exertion (RPE) using Borg's Scale. If a participant's RPE rating exceeds 15 (i.e. Hard (heavy)) or the physical therapist determines that the gait quality is poor, the treadmill walking will be stopped. The treadmill is equipped with a wrist-band that, if detached from the treadmill, will stop the treadmill. Furthermore, there are two buttons on the treadmill that will allow the participant or physical therapist to stop the treadmill at any time. Each participant will be oriented to these safety features prior to starting treadmill walking. Both treadmill walking and cueing have been used to reduce gait variability and improve spatiotemporal gait parameters in people with PD without STN-DBS. To gain more information about how participants perceive the fatigue and challenges associated with each exercise, we will use a numeric rating scale (NRS). Participants will be asked on a scale of 0-10 how fatiguing and challenging they feel each exercise was after completing it. The attachment (NRS) will be shown to the participant each time the question is asked. Each participant's ratings will be recorded on the physical therapy intervention protocol document. Finally, participants in the physical therapy group will be provided a home exercise program (HEP). The HEP will be designed to maintain or improve lower extremity strength. Lower extremity strengthening exercises will include repeated sit-to-stand, heel raises in standing, hip abduction, and standing half squats. Participants will receive a detailed handout that includes instructions on how to correctly and safely complete each exercise. Participants will perform the HEP twice weekly on days in which they are not attending a physical therapy session. Additionally, participants in the PT group will be asked to complete the HEP twice weekly during the 4 weeks between the post-test and follow-up assessments. Participants will track performance and completion of the HEP using the HEP Checklist. During the intervention, the forms will be returned to the study team at each physical therapy session. During the 4-week follow up period, each participant in the PT group will return the forms at the follow-up assessment visit. In addition to physical therapy, participants will be allowed to adjust anti-PD medication and STN-DBS settings as determined by their neurologist. To measure safety, participants assigned to the PT group will complete an Adverse Events tracking form with the physical therapist weekly during the intervention.

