### **Power**

To our knowledge, there are no intervention studies that specifically examined the efficacy of physical therapy on balance in people with PD with STN-DBS. Given that this is a pilot study, the authors chose an effect size that would be meaningful and required to support moving forward with a larger trial. As such, with a medium effect size of 0.25 (Cohen's  $f$ ) and an alpha level of 0.05, 14 participants per group will provide 82% power to detect significant differences between or within groups for the primary preliminary efficacy outcome (i.e., BESTest). Factoring in a potential for 20% dropout attrition rate based on prior studies, we plan to recruit 17 participants per group. This pilot study is not powered to detect significant differences in the number of adverse events between groups.

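### Adverse events are summarised only as a total per arm; participants affected and events per person-week should be added, and in-session events listed

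*Combined protocol and SAP*

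**What the plan says.** Under Specific Aims, the safety variable for Aim 1 is the number of adverse events, with falls and orthopedic injuries as examples. Hypothesis 1 is a between-arm statement: "We hypothesize that participants with STN-DBS plus PT will not report more adverse effects than those with STN-DBS only". The Statistical Analysis Plan section answers it with one sentence: "The total number of adverse events will be reported for each group allowing for qualitative comparisons". The Power section adds that the pilot is not powered for adverse-event differences.

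The data behind the total are weekly. Under Safety and Adverse Events: "The Adverse Event tracking form will be completed weekly with every participant". In the PT arm, "participants assigned to the PT group will complete an Adverse Events tracking form with the physical therapist weekly during the intervention"; in the control arm, "those assigned the control group will be called weekly and will complete the Adverse Events tracking form over the phone".

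Exposure to supervised exercise differs by design: "Participants in the PT group will receive 8 weeks of the intervention, meeting 2 times per week for one hour each session". Interim Monitoring and Early Stopping gives, as its mark of an unsafe intervention, "more than 2 falls across multiple individuals are occurring within the intervention sessions". The analysis section gives those in-session events no line of their own.

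On numbers, the Power section needs 14 per group and then says: "Factoring in a potential for 20% dropout attrition rate based on prior studies, we plan to recruit 17 participants per group".

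**The concern.** When the only comparison is qualitative, the descriptive summary is the entire safety analysis. A raw total has three gaps here.

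- It does not show how events are spread over people. With 14 to 17 per arm, one frequent faller can decide which arm looks worse.
- It has no denominator. An arm that loses people has fewer weeks in which events can be recorded, and so a lower total at the same weekly rate.
- It merges in-session events with all others, although the monitoring section treats falls in sessions as the sign that the intervention is unsafe.

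The Background makes later efficacy studies conditional on the intervention being safe and feasible, so a readable safety summary is a main product of this pilot.

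**Working it through.** The plan states no adverse-event rate, margin or power, so there is no safety figure to reproduce. The checks use the plan's own numbers where it has them and labelled assumptions elsewhere.

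**Inputs from the documents.** 17 recruited and 14 evaluable per arm (Power), so the allowance is 17 − 14 = 3 losses per arm; 8 weeks, 2 sessions a week, 16 sessions in all (Intervention; Measures).

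**1. Dropout.** Expected total = weekly rate × person-weeks. Full retention gives 17 × 8 = 136 person-weeks.

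- 3 lost at week 0 from one arm only: 14 × 8 = 112; 112/136 = 0.82.
- 3 lost at week 4 from one arm only: 14 × 8 + 3 × 4 = 124; 124/136 = 0.91.
- Equal loss in both arms, as planned: ratio 1.0.

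Dividing events by person-weeks returns the expected ratio to 1.0 in each case.

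**2. Clustering.** Assumptions: 17 per arm; mean m of 0.5, 1 or 2 events per person over 8 weeks; either no clustering (Poisson) or negative binomial with k = 1, 0.5 or 0.3, where smaller k means more clustering. The arm total is Poisson(17m), or negative binomial with size 17k and p = k/(k+m). Participants affected is Binomial(17, π), with π = 1 − exp(−m), or 1 − (k/(k+m))^k.

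Chance that the larger count is at least twice the smaller when true rates are equal (from no clustering to k = 0.3):

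| m | Totals | Participants affected |
|---|---|---|
| 0.5 | 21% to 45% | 17% to 34% |
| 1 | 6% to 38% | 2% to 21% |
| 2 | 1% to 33% | 0% to 11% |

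Chance that the PT count is at least twice the control count when the true PT rate is double:

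| Control m | Totals | Participants affected |
|---|---|---|
| 0.5 | 52% to 54% | 30% to 32% |
| 1 | 51% to 53% | 7% to 20% |
| 2 | 51% to 52% | 0% to 11% |

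The tables must be read together. Participants affected gives fewer chance two-fold gaps, but it also responds less to real harm, partly because it cannot exceed 17. At control mean 1, a true doubling gives an expected ratio of participants affected of (1 − e^−2)/(1 − e^−1) = 0.865/0.632 = 1.37 without clustering, and 0.457/0.356 = 1.28 at k = 0.3.

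**3. In-session events.** The PT arm has up to 17 × 16 = 272 supervised sessions; controls have none. Take three in-session falls, the smallest count above two, and add them to equal out-of-session totals of 8, 17 or 34 (illustrative). The PT-to-control ratio of totals becomes 11/8 = 1.38, 20/17 = 1.18 or 37/34 = 1.09. A comparison confined to events outside sessions would show 1.0 each time.

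**4. Precision of the added proportion.** Exact (Clopper-Pearson) 95% intervals: 0 of 17 gives 0 to 1 − 0.025^(1/17) = 19.5%; 5 of 17 gives 10.3% to 56.0%; 0 of 14 gives 0 to 23.2%.

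**The case against.** The strongest reply is that the plan does what it says. The Aim 1 variable is the number of adverse events, the analysis reports that number by arm, the comparison is called qualitative, and lack of power is disclosed. This stands. A reader might infer that a test is missing or that the aim and the analysis conflict; the documents do not support that. Strictly, the Aim 1 sentence speaks only of determining safety; Hypothesis 1 and the opening purpose paragraph make the comparison.

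The second reply is that the extra summaries could be made later from the same forms. That is true, but the plan does not commit to them, and a summary chosen after the events are known is less convincing.

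Four stronger readings are tempting and should be resisted.

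- That participants affected is the better harm measure because it gives fewer chance two-fold gaps. The second table above shows the price: much lower sensitivity to a true doubling.
- That the main contrast should use only events outside sessions, where the arms are alike. Hypothesis 1 compares PT plus stimulation with stimulation alone, and falls during therapy are the harm most directly caused by it. Step 3 shows how such a contrast would remove them.
- That therapist contact in one arm and phone contact in the other biases the counts. The contact mode does differ, but form and frequency are the same, and nothing in the documents gives a size or direction.
- That the collection windows differ, because control calls have no stated end. Calls to week 12 would give 17 × 12 = 204 person-weeks against 136, but the safety section applies one weekly form to every participant, and a common window is the natural reading.

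The tracking form is not among the documents and may already record date and setting.

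**Conclusion.** The point holds as a cheap improvement to the descriptive safety summary. Totals alone do not show whether events are concentrated in a few people and do not allow for uneven follow-up. The dropout effect is modest: a ratio of 0.82 to 0.91 if all three losses fall in one arm, and none if losses are equal as planned. The clustering effect could be larger, but its size rests wholly on assumed rates and dispersion. The totals should remain the between-arm comparison, with all events counted; the added measures make them easier to interpret.

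**What to change.** In the Statistical Analysis Plan section, keep the total number of events per arm, in-session events included, as the between-arm comparison, and add from the existing weekly forms:

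1. per arm, the number of participants with at least one event and with at least one fall, each with an exact 95% confidence interval;
2. per arm, events per person-week of observation, over the same stated collection window in both arms;
3. for the PT arm, a separate line for events within therapy sessions, matching the monitoring section, without removing them from the total.

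The cost is a few lines of text and a slightly larger table, with no extra calls, visits or participants. If the form does not already record whether an event happened in a session, it needs one tick box. The downsides are wide intervals (even 0 of 17 has an upper limit of about 20%) and the lower sensitivity of participants affected, which the text should state.
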